6.3.2 Informed Consent

Phase 1A

Prior to the screening call, the research coordinator will send the prospective participant an email including a copy of the oral consent form (see “CDST - Oral consent preview email” attached). During the screening call, the research coordinator will inform prospective participants that the study seeks to develop a tool embedded in a headache diary to improve patient decision making regarding migraine management adherence. They will be informed that the study will last for one week, during which time they will receive popup notifications in a 3x/day headache diary. They will also be informed that, at the end of the week, they will participate in a focus group with the PI that may last up to an hour. They will be informed about compensation for participation. The research coordinator will obtain informed consent over the phone (see “CDST stamped Oral Consent Form”, previously approved) and send the participant a confirmation email (see “CDST - Oral consent confirmation email” attached).

Phase 1B

Prospective participants will be informed that the study seeks to develop a tool embedded in a headache diary to improve patient decision making regarding migraine management adherence. They will be informed that the study will last for one month, during which time they will receive popup notifications in a 1x/day headache diary. They will also be informed that, at the end of the month, they may participate in a focus group with the PI that may last up to an hour. They will be informed about compensation for participation. The prospective participant will electronically sign the consent form on REDCap, a secure web application for building and managing online surveys and databases. The research coordinator will send the participant a confirmation email after consent is obtained.

Phase 2 and 3

During the screening call, the research assistant supervised by the PI will inform prospective participants that the study seeks to understand how people manage their migraines, and what factors impact patient migraine management, using monthly surveys and a headache diary that will sound three times per day for three months. Prospective participants will also be informed that, if they meet inclusion criteria after three months, they will have the opportunity to continue in the study and be randomized to receive one of two kinds of education that will pop-up as notifications in their headache diary, with the goal of improving migraine management. Prospective participants will be informed that they would continue to take monthly surveys and a headache diary that will sound three times a day for an additional three months. Thus, the total potential length of study participation is 6 months. Participants will be informed about compensation for participation. If interested and eligible, the potential participant will be provided with an opportunity to provide online informed consent ("Informed Consent Phase 2.3" uploaded to the informed consent section of iRIS).

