6. METHODS

6.1 INTERVENTION

Intervention occurs only in Phase 3 of the study. All data collection will occur in REDCap (Research Electronic Data Capture), a secure, HIPAA-compliant electronic data capture system hosted by the Research Informatics Core at Einstein (53). Survey collection will occur in the participant's browser. Daily diary collection will occur using an app (Status/Post) developed for this study to connect participants seamlessly to REDCap using an Apple device. Participants who do not have an Apple device will be provided with a study iPod. Interventions will be delivered through the Status/Post app.

Participants will be randomized to receive either the 1) CDST or 2) Headache Education version of the Status/Post App.

- 1) The Clinical Decision Support Tool (CDST) version of the Status/Post app will include several education modules with companion reminders. Education modules are individualized websites linked to the app that provide a consistent source of information about migraine management. Reminders are just-in-time notifications the participant receives in response to their adherence behaviors throughout the study that briefly remind participants about the education they received in response to their behaviors.

All participants will receive the Medication module, designed to provide information regarding appropriate use of acute and preventive migraine medication. Participants will be assigned to one of three behavioral management education module based on their individual adherence to that behavioral management strategy during the Phase 2 of the study. The three behavioral management education modules are: Stress Management, Sleep Management, and Consistent Eating/Hydration. Each is designed to provide education about why the behavioral strategy is important for migraine management, and provide specific tools to help patients improve their behavioral migraine management adherence.

- 2) The Headache Education version of the Status/Post app will include several education modules available in the app designed to increase general knowledge about migraine, including 1) diagnostic criteria of migraine and other common headaches, 2) pathophysiology of migraine, and 3) common comorbidities of migraine and other headaches.

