6.1.4 Intervention Administration

During Phase 1, the CDST or Headache Education version of the app will be administered to participants for one week. During Phase 3, the CDST or Headache Education version of the app will be administered to participants for 3 months. In both Phases, participants will download the app to their personal Apple device, or to a study-provided Apple device. Participants will receive a series of education modules (Figure 6.1.4), and for participants in the CDST group, notifications in the app tailored based on diary entries, which occur three times daily.

Figure 6.1.4

Treatment fidelity is conceptualized as the app providing the education and reminders at the allocated times. The app will monitor this information internally during both Phase 1 and 3.

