If any of these procedures identify a potential adverse event, the participant will be called immediately to assess the potential adverse event. Participants who disclose potential adverse events to any study staff at any point during the study will immediately be reported to the PI, [name], Ph.D., clinical psychologist. If [name] is unavailable, [name], Ph.D., clinical psychology and Director of Clinical Training at Ferkauf Graduate School of Psychology, Yeshiva University ([contact]) will assess and determine the best course of action in the case of immediate participant distress. If the adverse event requires medical or professional intervention, the PI or [name] will immediately contact the participant's primary clinician at the MHC and develop an intervention plan and referral if necessary. If a participant experiences an adverse event, he or she will be given an opportunity to leave the study. Any SAEs that are possibly related to the study intervention will be reported to the IRB and NIH within 7 days. All AEs will be compiled and reported to the Einstein IRB and NIH in accordance with the Einstein IRB requirements.

The Data Safety Monitoring Committee (DSMC) will consist of Drs. [name]., Assistant Professor of Psychology, and [name]., Professor of Psychology, at Ferkauf Graduate School of Psychology, Yeshiva University. The DSMC has final authority regarding making decisions regarding continuation, revision or discontinuation of the research project. The DSMC will meet every six months. The unblinded research assistant will provide reports of adverse events and diary-recorded symptoms by group to the DSMC at minimum every six months. The DSMC will provide minutes of each meeting to the PI, including attendance, summary of the discussion, and any findings. The PI will be responsible for implementation of this Data Safety Monitoring Plan and will report directly to the Einstein IRB and the NIH.

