Phase 3: At the end of Phase 2, a research assistant supervised by the PI will evaluate each participant’s diary data to determine eligibility criteria for Phase 3. The research coordinator will reach out to each participant and inform them of their eligibility determination for Phase 3, and assess interest in continuing in the study. Participants who are eligible and interested in participating in Phase 3 will be randomized by an unblinded research assistant, who will have no contact with participants after randomization. The rest of the study staff will be unaware of each participant’s randomization status.

After randomization, the participant will be sent instructions for initialization of the intervention study app from the research coordinator. Participants will use the intervention version of the app for three months. During this time, participants will continue to complete the headache diary three times daily and complete monthly and endpoint surveys (see Figure 6.3.1).

The research coordinator will continue to email each participant bi-weekly and provide feedback on diary days completed, offer troubleshooting for the application, and assess for adverse events, and reach out if the participant fails to record data for 2 days in a row. After the conclusion of Phase 3, the research coordinator will thank participants for their study participation and provide a compensation gift card (\$20 for Month 6 surveys, \$10 for Months 4 and 5 surveys, and \$0.50 for each diary entry, with total possible compensation of \$85).

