7.1 Ethical Considerations

There is no deception in this study. All participants will be told that they will receive additional messages in their headache diary, and that the purpose of the study is to examine what kinds of messages improve adherence to migraine management. Each participant will receive education that could improve migraine management sent via the diary app. Some participants will receive a CDST, whereas others will receive more general Headache Education. Group assignment will be random.

Subjects will be made aware that nominal payment will be provided as compensation. Gift Cards will be sent after participation Phase 1A (\$30), Phase 1B (participants will be entered into a raffle for one of three \$200 Gift Cards), Phase 2 (up to \$105), and Phase 3 (up to \$85).

The proposed research does not target vulnerable populations and will not involve any of the following vulnerable populations: fetuses, neonates, children, pregnant women, prisoners, institutionalized individuals.

Information about patient diagnoses, medications, and health care utilization will be obtained from the MHC electronic health record. Participants will provide data through electronic surveys given either semi-monthly, monthly, or as part of a diary given 3 times daily. Participant data will be collected via REDCap, a secure online data capture software, through the headache diary application. These data, which will not contain identifiable information, will be kept in a password protected database on a password-protected file on lab computers. Only the PI, Research Coordinator and research assistant will have access to these files. Data will be de-identified and converted to electronic databases and stored in password-protected files on a password-protected computer in the locked lab. A list linking participant identification numbers will be kept in a password-protected file on the password-protected hard drive in [name] lab, and will be destroyed immediately after all data has been entered (no more than 6 months after the end of data collection).

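### Consent describes pop-up notifications for both arms but the delivery text gives them only to CDST, an avoidable cue to allocation when every primary outcome is self-reported; the claimed staff blind has no described safeguard

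*Combined protocol and SAP*

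**What the plan says.** What participants are told. Section 6.3.2 says that those who qualify for Phase 3 will be "randomized to receive one of two kinds of education that will pop-up as notifications in their headache diary". Section 7.1 opens with "There is no deception in this study" and continues: "All participants will be told that they will receive additional messages in their headache diary". It adds that the purpose is to learn which kinds of message improve adherence.

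What is delivered. Section 6.1.4 (Intervention Administration) says that participants receive education modules and, "for participants in the CDST group, notifications in the app tailored based on diary entries, which occur three times daily". Section 6.1 draws the same line. The CDST version "will include several education modules with companion reminders"; the Headache Education version "will include several education modules available in the app designed to increase general knowledge about migraine", with no reminder or notification mentioned.

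How outcomes arise. Sections 5.2.1 and 6.2.1 (Efficacy) take every primary outcome from the participant's own electronic diary.

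Who is said to be unaware. Section 6.3.1 limits knowledge of allocation to the assistant who randomizes and says that the remaining staff do not know it. The next paragraph says that "the participant will be sent instructions for initialization of the intervention study app from the research coordinator", and the coordinator then contacts each participant every two weeks with diary feedback, app help and adverse-event questions. Sections 6.2.1.2 and 7.7 send by-group adverse-event and symptom reports to the DSMC, and then: "The DSMC will provide minutes of each meeting to the PI, including attendance, summary of the discussion, and any findings".

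**The concern.** The consent text and the delivery text do not agree on what the control arm gets. A control who has been led to expect pop-ups and sees none has a reason to wonder about allocation, or to report a fault to the coordinator. Either can happen while that person is entering the data that form every primary outcome, knowing that the study asks which messages work. Some visible difference between the two apps is inherent in the comparison; a promise that one arm may not see kept is an extra cue that wording alone could remove.

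The staff side is separate. The plan does claim a blind there, and then gives the coordinator and the principal investigator tasks through which allocation could become known, without saying how that is prevented.

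At stake is the reading of the randomized comparison, which Section 3.3.1 (Potential Benefits) says will supply initial effect sizes. A reporting difference between arms would look the same as an effect of CDST.

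**Working it through.** **1. Consent against delivery**

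- Told to participants: both kinds of education pop up (6.3.2); everyone gets extra messages (7.1).
- Delivered: modules to both arms, notifications to CDST (6.1.4); reminders listed for CDST, none listed for control (6.1).

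There are two possibilities. If control modules arrive without a pop-up, 6.3.2 and 7.1 are untrue for the 30 of 60 randomized to control. If control modules are announced by pop-up, 6.1 and 6.1.4 are incomplete. Either way, part of the text must change.

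**2. Staff blind against staff tasks**

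| Task | Stated | Not stated |
|---|---|---|
| Coordinator sends app set-up instructions (6.3.1) | Yes | Whether they differ by arm or show the version |
| Coordinator troubleshoots the app every two weeks (6.3.1) | Yes | How a query about missing pop-ups is answered without learning the arm |
| Investigator reads individual diaries monthly (6.2.1.2) | Yes | Whether the view shows app version |
| Investigator receives DSMC minutes after by-group review (6.2.1.2, 7.7) | Yes | Whether by-group content is held back |

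**3. Scale**

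Inputs: 30 per group, 80% power for an odds ratio (OR) of 1.28, proportion p = 0.37 (stress management, given for Phase 2), cumulative dropout 0.073, 0.172 and 0.216, and correlation at most 0.6 (all 6.4.2); two-sided 0.05 (6.4.1).

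*The plan's own figure.* Detectable OR = exp[(1.960 + 0.842) × √(V × (1/30 + 1/30) / (0.37 × 0.63))], where V is the variance factor for the mean of m daily reports. With dropout spread evenly within each 30-day month, m = 30 × (0.9635 + 0.8775 + 0.806) = 79.4.

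- Independent days: V = 1/79.4 = 0.0126, OR 1.18.
- AR(1) 0.6: V = (1/m)[1 + 2Σ(1 − k/m)0.6^k] = 0.049, OR 1.39.
- Exchangeable 0.6: V = (1 + 78.4 × 0.6)/79.4 = 0.605, OR 3.21.
- Exchangeable of about 0.015 gives 1.28.

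So 1.28 is not reproduced from the stated inputs. The correlation structure is not given, so this is a failure to reproduce, not a proven error. The figure serves below only as a yardstick.

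*Reporting gap equal to that OR, with no change in behaviour.*

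- 0.43 against 0.37: (0.43/0.57)/(0.37/0.63) = 0.754/0.587 = 1.28.
- 0.42 against 0.37: 0.724/0.587 = 1.23.
- Exactly 1.28: odds 0.587 × 1.28 = 0.752, proportion 0.752/1.752 = 0.429. The gap is 5.9 points, or 0.059 × 90 = 5.3 of 90 diary days.
- Assumed base 0.20: 0.242, a gap of 4.2 points or 3.8 days. Assumed base 0.50: 0.561, a gap of 6.1 points or 5.5 days.

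*Chance of a significant result from reporting alone.* Taking the stated power at face value, SE = ln(1.28)/2.802 = 0.088. With reporting bias b and x = ln(b)/SE, the chance is 1 − Φ(1.960 − x) + Φ(−1.960 − x).

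| Assumed b | x | Chance |
|---|---|---|
| 1.10 | 1.08 | 19% |
| 1.15 | 1.59 | 35% |
| 1.20 | 2.07 | 54% |
| 1.28 | 2.80 | 80% |

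These depend on the stated power. Under exchangeable 0.6, SE = ln(3.21)/2.802 = 0.416, and b = 1.28 gives x = 0.59 and a chance of about 9%.

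**The case against.** The best defence is that the documents never say control modules arrive silently. Section 7.1 says that everyone's education is sent through the diary app. Section 6.1.4 defines fidelity as timed delivery of education as well as reminders. Phase 1A testers, who get either version, are told to expect pop-ups (6.3.1, 6.3.2). The figure with the module schedule is not available here, and that cannot count against the plan. This stands: a reader might infer a proven false promise, but the documents support only an unresolved conflict.

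A reader might also infer that controls can tell their arm. That goes too far. The consent text described in the protocol does not say that one arm lacks pop-ups, so a control who sees none may simply suspect a fault. No passage claims that participants are blinded, so no participant blind is contradicted. Neutral wording will not hide the difference between the apps or remove self-report.

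A third tempting reading is that the staff blind cannot hold. The documents do not show that the set-up instructions or the minutes reveal anyone's arm, and both versions run in one app. Routine contacts use named email templates and a fixed trigger of two missed days. Participants, not staff, enter the outcomes. Nor could by-group findings readily steer entry to Phase 3: eligibility is judged before randomization, from Phase 2 diaries, against numeric thresholds. Aggregate results do not identify individuals.

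On size, 0.37 is a Phase 2 figure for one strategy. Some outcomes are less open to impression than a yes/no item: sleep uses recorded times, and the evening diary collects eating by hour. Phase 3 is a pilot serving the secondary objective.

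What remains is the text conflict, and a claimed staff blind whose protection is nowhere described.

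**Conclusion.** The point holds in limited form. Sections 6.3.2 and 7.1 conflict with 6.1 and 6.1.4 on whether controls receive notifications and must be reconciled. As written, the conflict may give controls an avoidable cue to allocation, or send fault queries to the coordinator. The staff blind in 6.3.1 is at risk through the coordinator's app tasks and the investigator's DSMC minutes; it is not shown to fail.

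The size is an illustration. A reported difference of about 6 points at a base of 0.37 (4.2 to 6.1 points for assumed bases of 0.20 to 0.50) would equal the OR of 1.28. The documents give no estimate of reporting bias, and none is claimed here. The conversion treats 1.28 as an OR between group proportions; the planned random-effects model estimates a within-person OR, for which the matching gap would be smaller.

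This should be corrected because it is cheap and bears on how the randomized comparison is read. It does not invalidate the trial.

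**What to change.** (a) Reconcile 6.3.2, 7.1 and the consent form with 6.1 and 6.1.4. State in 6.1 how control modules are announced. Use consent wording that is true for both arms and identifies neither, for example that participants are allocated at random to one of two education programmes provided within the app, with no promise of pop-ups.

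(b) Send the set-up link as an automatic REDCap message carrying a coded app version, so that the coordinator does not handle the arm-specific version. Name who answers app faults in Phase 3. This should not be the unblinded assistant, whom 6.1.2 and 6.3.1 bar from participant contact after randomization.

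(c) Keep by-group DSMC material in closed minutes, and send the principal investigator only the recommendation and pooled findings.

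An end-of-study question asking participants and staff to guess the arm would be an optional check.

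Cost: a consent amendment, one automated message and a split of the DSMC minutes, with no more participants and no change to the intervention. Answering faults outside the coordinator may take some staff time. The downside is slightly less detailed consent wording about notifications.

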6.3.3 Screening

Phase 1

Participants will be screened for inclusion/exclusion criteria during a scheduled phone call by the Research Coordinator (see "CDST Screener Grid" previously approved). This call should take no longer than 20 minutes.

Phase 2 and 3

Participants will be pre-screened for inclusion/exclusion criteria through Clinical Looking Glass by the Research Coordinator (see "Phase 2-3 Screening Checklist 1.8.18" attached). Participants will be screened by a research assistant supervised by the PI during a scheduled phone call (see "Phase 2-3 Screening Checklist 1.8.18" attached). This call should take no longer than 30 minutes. Participants who self-report meeting study inclusion criteria will be enrolled in the study and monitored with a headache diary three times daily for 30 days. After 30 days, a research assistant supervised by the PI will confirm study inclusion criteria. If participants do not meet study inclusion criteria at this time, they will be informed and removed from the study and provided with appropriate gift card compensation (see "CDST-Thank you emails" attached).

6.3.4 Enrollment

Phase 1

After completing the phone informed consent, the research coordinator will enroll the participant in the study and assign them a random study identification number.

Phase 2 and 3

After potential subjects have completed the online informed consent document, the research coordinator will assign them a random study identification number and register the participant in the study in Einstein/Montefiore's EPIC medical records system.

6.3.5 On Study Visits

All study visits occur either over the phone or via scheduled REDCap data capture sessions, which are either accessed through the participant's email on any device, or through the study app on either the participant's personal Apple device or the study-provided Apple device.

Phase 1A & B

Screening

- Research coordinator will assess inclusion/exclusion criteria
- Approximately 20 minutes in length

App Testing

- Interact with CDST or Headache Education version of app 3 times daily for 7 days (Phase 1A) or 30 days (Phase 1B).
- Each diary entry will take between 1-5 minutes

Focus Group:

- At least one participant per focus group; Focus group led by the PI
- Up to 60 minutes in length
- Questions will focus on: 1) User Interface; 2) Message Content; 3) Message Delivery and Frequency, and 4) Overall Satisfaction

Phase 2 and 3

Screening

- Research assistant will assess inclusion/exclusion criteria with the supervision of the PI
- Approximately 30 minutes in length

Electronic Data Collection:

- App-based
- Phase 2: Month 0-Month 3
- Phase 3: Month 3-Month 6
- See schedule of assessments below

Table 6.1.3. Timing of Measures

Month 0 ~20 min.	Demographics Migraine Symptoms Medications Health literacy (Newest Vital Sign) E-health literacy (eHEALS) Pittsburgh Sleep Quality Index (first 4-items) Berlin Questionnaire
Month 0 Month 3 Month 7 ~40 min.	Migraine Disability Assessment Headache Management Self-Efficacy Acute Medication Self-Efficacy - Headache Study-Specific Self-Efficacy

	Outcome Expectancies Headache Specific Locus of Control Pain Catastrophizing Scale Five Factor Mindfulness Questionnaire Chronic Pain Acceptance Questionnaire
Monthly ~20 min.	Migraine Specific Quality of Life 2.1 PROMIS Interference Perceived Stress Scale PROMIS Anxiety PROMIS Depression PROMIS Sleep Disturbance Daily Stress Inventory
Daily	Morning (~3-5 min.) -Menstruation -Headache Symptoms -Acute Medication Usage -Sleep Behavior Afternoon (~1-2 min.) -Headache symptoms -Acute Medication usage Evening (~3-5 min.) -Preventive Medication Usage -Headache Symptoms -Acute Medication Usage -Eating and Hydration behavior -Stress Level and Management -Migraine Disability
Month 7 ~7 min.	Client Satisfaction Questionnaire Program Evaluation

